## 10. MEASUREMENT OF EFFECT

### 10.1 Antitumor Effect – Solid Tumors

For the purposes of this study, participants should be re-evaluated for response every 12 weeks.

Response and progression will be evaluated in this study using the new international criteria proposed by the Response Evaluation Criteria in Solid Tumors (RECIST) guideline (version 1.1) [Eur J Ca 45:228-247, 2009]. Changes in the largest diameter (unidimensional measurement) of the tumor lesions and the shortest diameter in the case of malignant lymph nodes are used in the RECIST criteria.

#### 10.1.1 Definitions

Evaluable for Target Disease Response. Only those participants who have measurable disease present at baseline, have received at least one cycle of therapy, and have had their disease re-evaluated will be considered evaluable for target disease response. These participants will have their response classified according to the definitions stated below. (Note: Participants who exhibit objective disease progression prior to the end of cycle 1 will also be considered evaluable.)

Evaluable Non-Target Disease Response. Participants who have lesions present at baseline that are evaluable but do not meet the definitions of measurable disease, have received at least one cycle of therapy, and have had their disease re-evaluated will be considered evaluable for non-target disease. The response assessment is based on the presence, absence, or unequivocal progression of the lesions.

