## **3. PARTICIPANT SELECTION**

### **3.1 Eligibility Criteria**

3.1.1 Participants must have histologically or cytologically confirmed low- to intermediate-grade neuroendocrine tumor (carcinoid tumor).

- 3.1.2 Carcinoid tumors of any site are eligible. Patients with pancreatic neuroendocrine tumors are excluded.
- 3.1.3 Participants must have measurable disease, defined as at least one lesion that can be accurately measured in at least one dimension (longest diameter to be recorded for non-nodal lesions and short axis for nodal lesions) as  $\geq 20$  mm with conventional techniques or as  $\geq 10$  mm with spiral CT scan, MRI, or calipers by clinical exam. See Section 10 for the evaluation of measurable disease.
- 3.1.4 Locally advanced, unresectable or metastatic disease.
- 3.1.5 Patients must have evidence of radiographic disease progression within the past 12 months. Progressive disease by RECIST criteria is not required.
- 3.1.6 Age  $\geq 18$  years.
- 3.1.7 ECOG performance status 0-1 (see Appendix A).
- 3.1.8 Participants must have normal organ and marrow function as defined below:
- |                             |  |
|-----------------------------|--|
| - absolute neutrophil count | $\geq 1,000/\text{mm}^3$   |
| - platelets                 | $\geq 100,000/\text{mm}^3$   |
| - hemoglobin                | $\geq 9\text{ g/dL}$   |
| - total bilirubin           | $\leq 1.5 \times$ institutional upper limit of normal  |
| - AST(SGOT)/ALT(SGPT)       | $\leq 3 \times$ institutional upper limit of normal, or $\leq 5 \times$ institutional upper limit of normal in the setting of liver metastases   |
| - creatinine                | $\leq 1.5 \times$ upper limit of normal  |
| - urinary protein           | $\leq 1+$ on dipstick or routine urinalysis (if urine dipstick or routine urinalysis is 2+, a 24-hour urine collection for protein must demonstrate $<1000$ mg of protein in 24 hours)   |
| - coagulation function      | Adequate coagulation function as defined by International Normalized Ratio (INR) $\leq 1.5$ and a partial thromboplastin time (PTT) $< 1.5 \times$ institutional upper limit of normal. Patients on full-dose anticoagulation must be on a stable dose (minimum duration 14 days) of oral anticoagulant or low molecular weight heparin. |

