## **5.3 Agent Administration**

### **5.3.1 Ramucirumab**

Ramucirumab will be administered as a 1-hour IV infusion on Days 1 and 15 of a 28-day cycle. The infusion rate of ramucirumab should not exceed 25 mg/min.

Premedication: Prior to each infusion of ramucirumab, premedicate all patients with an intravenous histamine H1 antagonist, such as diphenhydramine hydrochloride. Additional premedication may be provided at investigator discretion.

If a patient experiences a Grade 1 or 2 infusion-related reaction (IRR), premedication **must** be given for all subsequent infusions, as outlined in Section 6 of the protocol.

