### **12.4 Analysis of Secondary Endpoints**

Secondary objectives of this study are to:

- To determine the safety and tolerability of ramucirumab in combination with somatostatin analog therapy in patients with advanced carcinoid tumors. We will assess the rate of adverse events (as defined by Common Terminology Criteria for Adverse Events (CTCAE), version 4.0), associated with treatment.

Because adverse events associated with the combination of ramucirumab and a somatostatin analog have not examined previously, toxicity and adverse events will be examined in the first 10 patients who complete one cycle of therapy before expanding enrollment.

- To assess the overall radiographic and biochemical response rate associated with ramucirumab in patients with advanced carcinoid tumors. We will estimate the response rate and provide the associated 95% confidence interval.

- To assess the overall survival duration of patients with advanced carcinoid tumors treated with ramucirumab. We will use the Kaplan-Meier method to estimate the distribution of overall survival.

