### 12.5.2 Evaluation of the Primary Efficacy Endpoint

Analyses will be conducted on an intent-to-treat basis. Specifically, all eligible participants included in the study must be assessed for response/outcome to therapy, even if there are major protocol therapy deviations.

Subanalyses may then be performed on the basis of a subset of participants, excluding those for whom major protocol deviations have been identified (e.g., early death due to other reasons, early discontinuation of treatment, major protocol violations, etc.). However, these subanalyses may not serve as the basis for drawing conclusions concerning treatment efficacy, and the reasons for excluding participants from the analysis should be clearly reported. If applicable to the endpoint, the 95% confidence intervals should also be provided.

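### Does the unnamed denominator in section 12.4 put the radiographic response rate at real risk of being overstated?

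*Combined protocol and SAP*

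**What the plan says.** Section 12.4 gives the whole analysis of response in one sentence: "We will estimate the response rate and provide the associated 95% confidence interval". It names no denominator, no interval method and no rule for patients who were never re-imaged.

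Two other places bear on the denominator.

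- Section 10.1.1 limits classification of target response to participants with baseline measurable disease who "have received at least one cycle of therapy, and have had their disease re-evaluated will be considered evaluable for target disease response". A note adds early progressors: "Participants who exhibit objective disease progression prior to the end of cycle 1 will also be considered evaluable".
- Section 12.5.2 states that "Analyses will be conducted on an intent-to-treat basis" and that "all eligible participants included in the study must be assessed for response/outcome to therapy, even if there are major protocol therapy deviations". Its second paragraph allows analyses of subsets, for example without patients who died early of other causes or stopped treatment early. It does not let those analyses carry efficacy conclusions, and it asks for the reasons for exclusion to be reported. The sub-heading refers to the primary efficacy endpoint; the parent heading, 12.5, covers reporting and exclusions in general.

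On timing, section 10.1 says "participants should be re-evaluated for response every 12 weeks".

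**The concern.** Response is a secondary endpoint, so a literal reader could hold that 12.5.2 governs only PFS. Section 10.1.1 would then be the only text on who counts for response. An evaluable-only denominator removes patients who die, withdraw or are lost before any scan. None of them can be a documented responder, so leaving them out can only raise the rate or leave it at zero. Two analysts could then report different rates from the same data, and the choice might be made with the results in view. The figure would be read next to PFS when a later randomised study is considered (section 2.3), so an inflated value would not be welcome.

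**Working it through.** **The plan's own figure.** None is given for response. The only sample-size figure is N = 43 for PFS (section 12.2: median 8 against 12 months, one-sided 0.05, 80% power). It reproduces with a one-sample exponential log-hazard test. Events = (1.645 + 0.842)² / (ln 1.5)² = 37.6. With uniform accrual over 24 months and 24 further months of follow-up, the probability of an event under a 12-month median is 0.865, so N = 37.6 / 0.865 = 43.5. The response denominator does not enter this calculation.

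**Which text governs.** Section 10.1.1 sits in the measurement chapter and says whose target response is classified. It mentions no rate, denominator or analysis set. Section 12.5.2 sits in the statistical chapter, sets an analysis population, and covers response/outcome in its text. Its remark on giving 95% intervals where the endpoint calls for them also suggests more than one endpoint. Section 4.1 cancels the registration of anyone who never receives protocol therapy, so all eligible participants are in effect all eligible treated participants.

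**Who could drop out under 10.1.1.**

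- *Measurable disease.* Section 3.1.3 already requires it ("Participants must have measurable disease"). There is one wrinkle. Section 3.1.3 gives 10 mm on spiral CT without a separate nodal cut-off, while section 10.1.2 asks for 15 mm in short axis for nodes. A patient whose only lesion is a node between those sizes could pass one and fail the other, although 3.1.3 refers the reader to Section 10.
- *Re-evaluation.* The first scheduled restaging is at 12 weeks = 84 days = 3 cycles of 28 days. The Study Calendar also marks radiographic evaluation at the off-treatment visit, and section 5.6 continues imaging every 12 weeks after early discontinuation until progression or new therapy. The patients left without any scan are mainly early deaths, withdrawals of consent, losses to follow-up and missed scans.
- *One cycle.* A cycle has two infusions ("Ramucirumab will be administered as a 1-hour IV infusion on Days 1 and 15 of a 28-day cycle"). The plan does not say whether one infusion counts as a cycle.

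**Size.** Let x be the number of responders and m the number of unscanned patients. The documents give neither, so both are assumed. I also assume that all 43 are eligible and treated. The rate over everyone is x/43 and over the evaluable set x/(43 − m), so the ratio is 43/(43 − m): 1.05 for m = 2, 1.10 for m = 4, 1.16 for m = 6 and 1.26 for m = 9. Values of 2 and 4 responders give 4.7% and 9.3%, close to the 4% and 9% that section 12.2 quotes for targeted agents in pancreatic tumours. Intervals are exact (Clopper-Pearson) 95%.

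| x | m = 0 | m = 2 | m = 4 | m = 6 | m = 9 |
|---|---|---|---|---|---|
| 0 | 0.0% (0.0–8.2) | 0.0% (0.0–8.6) | 0.0% (0.0–9.0) | 0.0% (0.0–9.5) | 0.0% (0.0–10.3) |
| 2 | 4.7% (0.6–15.8) | 4.9% (0.6–16.5) | 5.1% (0.6–17.3) | 5.4% (0.7–18.2) | 5.9% (0.7–19.7) |
| 4 | 9.3% (2.6–22.1) | 9.8% (2.7–23.1) | 10.3% (2.9–24.2) | 10.8% (3.0–25.4) | 11.8% (3.3–27.5) |

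With 2 unscanned patients the estimate rises by 0.2 points (x = 2) or 0.5 points (x = 4). With 9 unscanned, which is 21% of 43, it rises by 1.2 or 2.5 points. The full-denominator intervals are 15.8 − 0.6 = 15.2 and 22.1 − 2.6 = 19.5 points wide.

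**The case for a change.** The best case for a change is that the text leaves a choice open and closing it costs almost nothing. Section 12.4 is silent, the sub-heading of 12.5.2 names another endpoint, and even the body of 12.5.2 does not say that a patient without a scan counts as a non-responder. All of that is true. A sentence linking 12.4 to the 12.5.2 population would be harmless.

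It does not follow that the plan must be amended. Once the population is intent-to-treat, a patient with no documented response has no place in the numerator and stays in the denominator, which is the usual convention. The reverse choice, presenting an evaluable-only rate as the efficacy result, would go against the second paragraph of 12.5.2. If such a rate were published, the reasons for exclusion would have to be reported, so a reader could recover the full-denominator figure.

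The one-cycle condition could also discard a result that was actually observed, and there the direction is not fixed. If one of 4 responders were among 2 patients dropped, the rate would be 3/41 = 7.3% instead of 9.3%. That requires a response after about one infusion and a particular reading of an undefined term. Nothing in the documents makes it likely, and the intent-to-treat rule would keep that patient in.

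**Conclusion.** The gap is real, but it is missing detail and not a flaw. The upward bias exists only if the 10.1.1 group is taken as the denominator. No section says it will be, and the plan's general rule on analysis populations points the other way. With imaging due at the end of treatment and continued afterwards, few patients should be left unscanned. The plausible shift is therefore a few tenths of a point: 0.2 to 0.5 points with 2 unscanned patients and 2 to 4 responders, and none in the estimate with no responders. Section 2.1 itself describes response rates with VEGF pathway inhibitors in carcinoid as low. The shift is small beside an interval 15 to 20 points wide, on a descriptive secondary endpoint with no success threshold. These sizes rest on assumed counts of responders and unscanned patients and on 43 eligible, treated participants. The PFS conclusion, its power and the sample size do not depend on it. No change is called for.

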#### 10.1.2 Disease Parameters

Measurable disease. Measurable lesions are defined as those that can be accurately measured in at least one dimension (longest diameter to be recorded) as  $\geq 20$  mm by chest x-ray or  $\geq 10$  mm with CT scan, MRI, or calipers by clinical exam. All tumor

measurements must be recorded in millimeters (or decimal fractions of centimeters).

Note: Tumor lesions that are situated in a previously irradiated area might or might not be considered measurable.

Malignant lymph nodes. To be considered pathologically enlarged and measurable, a lymph node must be  $\geq 15$  mm in short axis when assessed by CT scan (CT scan slice thickness recommended to be no greater than 5 mm). At baseline and in follow-up, only the short axis will be measured and followed.

Non-measurable disease. All other lesions (or sites of disease), including small lesions (longest diameter  $< 10$  mm or pathological lymph nodes with  $\geq 10$  to  $< 15$  mm short axis), are considered non-measurable disease. Bone lesions, leptomeningeal disease, ascites, pleural/pericardial effusions, lymphangitis cutis/pulmonitis, inflammatory breast disease, abdominal masses (not followed by CT or MRI), and cystic lesions are all considered non-measurable.

Note: Cystic lesions that meet the criteria for radiographically defined simple cysts should not be considered as malignant lesions (neither measurable nor non-measurable) since they are, by definition, simple cysts.

‘Cystic lesions’ thought to represent cystic metastases can be considered as measurable lesions, if they meet the definition of measurability described above. However, if non-cystic lesions are present in the same participant, these are preferred for selection as target lesions.

Target lesions. All measurable lesions up to a maximum of 2 lesions per organ and 5 lesions in total, representative of all involved organs, should be identified as **target lesions** and recorded and measured at baseline. Target lesions should be selected on the basis of their size (lesions with the longest diameter), be representative of all involved organs, but in addition should be those that lend themselves to reproducible repeated measurements. It may be the case that, on occasion, the largest lesion does not lend itself to reproducible measurement in which circumstance the next largest lesion which can be measured reproducibly should be selected. A sum of the diameters (longest for non-nodal lesions, short axis for nodal lesions) for all target lesions will be calculated and reported as the baseline sum diameters. If lymph nodes are to be included in the sum, then only the short axis is added into the sum. The baseline sum diameters will be used as reference to further characterize any objective tumor regression in the measurable dimension of the disease.

Non-target lesions. All other lesions (or sites of disease) including any measurable lesions over and above the 5 target lesions should be identified as **non-target lesions** and should also be recorded at baseline. Measurements of these lesions are not required, but the presence, absence, or in rare cases unequivocal progression of each should be noted throughout follow up.

### **10.1.3 Methods for Evaluation of Disease**

All measurements should be taken and recorded in metric notation using a ruler, calipers, or a digital measurement tool. All baseline evaluations should be performed as closely as possible to the beginning of treatment and never more than 4 weeks before the beginning of the treatment.

The same method of assessment and the same technique should be used to characterize each identified and reported lesion at baseline and during follow-up. Imaging-based evaluation is preferred to evaluation by clinical examination unless the lesion(s) being followed cannot be imaged but are assessable by clinical exam.

**Clinical lesions.** Clinical lesions will only be considered measurable when they are superficial (e.g., skin nodules and palpable lymph nodes) and  $\geq 10$  mm in diameter as assessed using calipers (e.g., skin nodules). In the case of skin lesions, documentation by color photography, including a ruler to estimate the size of the lesion, is recommended.

**Conventional CT and MRI.** This guideline has defined measurability of lesions on CT scan based on the assumption that CT thickness is 5mm or less. If CT scans have slice thickness greater than 5 mm, the minimum size of a measurable lesion should be twice the slice thickness. MRI is also acceptable in certain situations (e.g. for body scans).

Use of MRI remains a complex issue. MRI has excellent contrast, spatial, and temporal resolution; however, there are many image acquisition variables involved in MRI, which greatly impact image quality, lesion conspicuity, and measurement. Furthermore, the availability of MRI is variable globally. As with CT, if an MRI is performed, the technical specifications of the scanning sequences used should be optimized for the evaluation of the type and site of disease. Furthermore, as with CT, the modality used at follow-up should be the same as was used at baseline and the lesions should be measured/assessed on the same pulse sequence. It is beyond the scope of the RECIST guidelines to prescribe specific MRI pulse sequence parameters for all scanners, body parts, and diseases. Ideally, the same type of scanner should be used and the image acquisition protocol should be followed as closely as possible to prior scans. Body scans should be performed with breath-hold scanning techniques, if possible.

**FDG-PET.** While FDG-PET response assessments need additional study, it is sometimes reasonable to incorporate the use of FDG-PET scanning to complement CT scanning in assessment of progression (particularly possible 'new' disease). New lesions on the basis of FDG-PET imaging can be identified according to the following algorithm:

- (a) Negative FDG-PET at baseline, with a positive FDG-PET at follow-up is a sign of PD based on a new lesion.
- (b) No FDG-PET at baseline and a positive FDG-PET at follow-up: If the positive FDG-PET at follow-up corresponds to a new site of disease confirmed by CT, this is PD. If the positive FDG-PET at follow-up is not confirmed as a new site of disease on CT, additional follow-up CT scans are needed to determine if there is truly

progression occurring at that site (if so, the date of PD will be the date of the initial abnormal FDG-PET scan). If the positive FDG-PET at follow-up corresponds to a pre-existing site of disease on CT that is not progressing on the basis of the anatomic images, this is not PD.

(c) FDG-PET may be used to upgrade a response to a CR in a manner similar to a biopsy in cases where a residual radiographic abnormality is thought to represent fibrosis or scarring. The use of FDG-PET in this circumstance should be prospectively described in the protocol and supported by disease-specific medical literature for the indication. However, it must be acknowledged that both approaches may lead to false positive CR due to limitations of FDG-PET and biopsy resolution/sensitivity.

Note: A 'positive' FDG-PET scan lesion means one which is FDG avid with an uptake greater than twice that of the surrounding tissue on the attenuation corrected image.

PET-CT. At present, the low dose or attenuation correction CT portion of a combined PET-CT is not always of optimal diagnostic CT quality for use with RECIST measurements. However, if the site can document that the CT performed as part of a PET-CT is of identical diagnostic quality to a diagnostic CT (with IV and oral contrast), then the CT portion of the PET-CT can be used for RECIST measurements and can be used interchangeably with conventional CT in accurately measuring cancer lesions over time. Note, however, that the PET portion of the CT introduces additional data which may bias an investigator if it is not routinely or serially performed.

Ultrasound. Ultrasound is not useful in assessment of lesion size and should not be used as a method of measurement. Ultrasound examinations cannot be reproduced in their entirety for independent review at a later date and, because they are operator dependent, it cannot be guaranteed that the same technique and measurements will be taken from one assessment to the next. If new lesions are identified by ultrasound in the course of the study, confirmation by CT or MRI is advised. If there is concern about radiation exposure from CT, MRI may be used instead of CT in selected instances.

Endoscopy, Laparoscopy. The utilization of these techniques for objective tumor evaluation is not advised. However, such techniques may be useful to confirm complete pathological response when biopsies are obtained or to determine relapse in trials where recurrence following complete response (CR) or surgical resection is an endpoint.

Tumor markers. Tumor markers alone cannot be used to assess response. If markers are initially above the upper normal limit, they must normalize for a participant to be considered in complete clinical response. Specific guidelines for both CA-125 response (in recurrent ovarian cancer) and PSA response (in recurrent prostate cancer) have been published [*JNCI* 96:487-488, 2004; *J Clin Oncol* 17, 3461-3467, 1999; *J Clin Oncol* 26:1148-1159, 2008]. In addition, the Gynecologic Cancer Intergroup has developed CA-125 progression criteria which are to be integrated with objective tumor assessment for use in first-line trials in ovarian cancer [*JNCI* 92:1534-1535, 2000].

Cytology, Histology. These techniques can be used to differentiate between partial responses (PR) and complete responses (CR) in rare cases (e.g., residual lesions in tumor types, such as germ cell tumors, where known residual benign tumors can remain).

The cytological confirmation of the neoplastic origin of any effusion that appears or worsens during treatment when the measurable tumor has met criteria for response or stable disease is mandatory to differentiate between response or stable disease (an effusion may be a side effect of the treatment) and progressive disease

